## Formulas for MELD, CPT, and Maddrey's DF

Clinical assessments for ascites and hepatic encephalopathy (to calculate CPT scores) and the Covance laboratory collection dates for each laboratory test required for MELD and CPT scores are recorded on the CPC\_MELD eCRF. Formulas for calculation of MELD score, CPT score, and Maddrey's DF are described in Section 6.2.8 of this SAP.

Baseline disease characteristics will be summarized by treatment group and overall using descriptive statistics for continuous variables and using number and percentage of subjects for categorical variables. Summaries of baseline characteristics will be provided for the Safety Analysis Set and Full Analysis Set.

No formal statistical testing is planned.

A by-subject listing of baseline characteristics will be provided by subject ID in ascending order.

## 5.3. Prior Corticosteroids for Treatment of Alcoholic Hepatitis

Corticosteroids could be administered for  $\leq 3$  days prior to starting study drug per protocol. Medications with ATC class level 2 = "Corticosteroids for systemic use" that started on Study Days -3, -2, or -1 and stopped on Study Day -1 or 1 will be included. Subject ID PPD started Urbason on Study Day -7 (protocol violation) and is included in the listing and summary table. The indication for the drug entered on the CM eCRF will be checked to ensure that it is consistent with administration for an indication of alcoholic hepatitis. Corticosteroids used to treat alcoholic hepatitis prior to starting study drug will be summarized by preferred drug name.

Prior corticosteroid medications used to treat AH will be provided in a by-subject listing sorted by subject ID number and administration date in chronological order.

## 5.4. Medical History and Baseline Infections

General medical history data will be collected at screening and listed only. General medical history data will not be coded. Subjects with baseline infections will have a checkbox marked on the MH eCRF to denote baseline infection events, and baseline infections will be listed separately. Results from cultures, x-rays, and ascitic fluid neutrophil cell counts (ie, > 250 cells/mm^3) for spontaneous bacterial peritonitis (SBP) confirming reported infections during the screening period will be included on this listing.

Prior medications that were used to treat baseline infections will be identified as drugs with a pull down indication of "infection" on the CM eCRF. Medications with an end date prior to screening date or a start date that is after the first dosing date of SEL/PLA will be excluded.

Listings will be provided for chest X-rays, and liver imaging performed at the screening visit.

# 6. EFFICACY ANALYSES

The primary efficacy analysis will include subjects in the FAS. A secondary analysis of efficacy will include subjects in the mITT analysis set. Subjects who receive a liver transplantation while enrolled in the study will have measurements collected up to the time of liver transplantation included in efficacy analyses; data collected after transplantation will be excluded from efficacy analyses.

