# 4.2.2. Adherence to Study Drug

The level of protocol defined adherence to each of the 2 study drugs will be determined by the total amount of study drug administered relative to the total amount of study drug expected to be administered based on what is specified in the protocol.

The level of adherence will be expressed as a percentage using the following formula:

On-Treatment Adherence (%) = 
$$\left(\frac{\text{Total Amount of Study Drug Administered}}{\text{Study Drug Expected to be Administered on Treatment}}\right) \times 100$$

Total amount of study drug administered will be the total number of pills dispensed minus the total number of pills returned. If a bottle (selonsertib/placebo) or carton (prednisolone) of study drug is not returned, the subject will be assumed to have not taken the pills.

Subjects are expected to take 28 tablets containing SEL (18 mg)/PLA and 112 tablets containing 10 mg of PRED; unless the subject is prematurely terminated from study drug due to death, lack of efficacy (meeting Lille score criteria [ie,  $\geq 0.56$  at Week 1 for prednisolone; or > 0.85 at Weeks 1, 2, 3, or 4 for both study drugs]), or does not have biopsy-proven severe AH on biopsy (ie, variable SDRGREAS\_STD equal to 'PW', 'PV', 'LE, or 'DT' on the study drug completion eCRF for an individual study drug and subject). Subjects who were transplanted while on study drug (eg, Subject ID PPD should also only have adherence calculated to their last dose date of study drug. Note that no subjects in the study had positive results for HBsAg, HCV RNA or HIV-1/HIV-2 per central laboratory assessment which was also a criteria for calculating adherence to last dose date. Subjects who do not complete individual study drug completion form, will have adherence for that study drug calculated to last dose date of individual study drug.

In addition, subjects meeting individual SEL/PLA subject stopping criteria for the study (eg, Grade 3 or higher treatment-emergent AE that is considered to be related to study drug and results in premature discontinuation of SEL/PLA, confirmed ALT or AST > 5 x baseline, confirmed total bilirubin > 3 x baseline or nadir, or ALT or AST > 500 U/L) who prematurely discontinued SEL/PLA will have adherence for SEL/PLA calculated to their last dose date of SEL/PLA (ie, Subject ID PPD for confirmed ALT > 5 x baseline).

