## 6.1. Secondary Efficacy Endpoints:

- Number (%) of subjects who die by Study Day 28 and by Weeks 8, 12, and 24
- Number (%) of subjects receiving a liver transplant by Study Day 28 and by Weeks 8, 12, and 24
- Summary of Lille score by visit through Week 4
- Number (%) of subjects with Lille response (score < 0.45) at Day 7 (eg, Week 1)
- Number (%) of subjects with Lille null response (score  $\ge 0.56$ ) at Day 7 (eg, Week 1)
- Mortality Risk at Months 2 and 6 based on Lille score response at Day 7 (eg, Week 1) and the baseline MELD score (continuous)
- Number (%) of subjects with infection while on study
- Number (%) of subjects with HRS while on study
- Length of initial hospital stay
- Change from baseline in liver biochemistry tests (ALT, AST, GGT, albumin, alkaline phosphatase, total bilirubin, direct bilirubin, and INR) by analysis visit through Week 24
- Change from baseline in prognostic indices (MELD, CPT, and Maddrey's DF) by analysis visit through Week 24

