#### 6.2. Analysis Methods for Secondary Efficacy Endpoints

#### 6.2.1. Death

The number (%) of subjects with a death by Study Day 28, and by Weeks 8, 12, and 24 will be displayed by treatment group. For the endpoint death by Day 28, subjects who die on/prior to Study Day 28 or are known to be alive through Study Day 28 will be included in the denominator for calculation of percentage of subjects with death. Subjects not followed through Day 28 will be summarized by their reason for premature discontinuation from study. A 2-sided

Fisher's exact test will be used to explore whether there are differences between treatment groups in percentage of subjects with death by Day 28. Deaths by Weeks 8, 12, and 24 will be summarized in the same manner as deaths by Study Day 28. Kaplan-Meier estimates of survival and the 95% CI (based on Greenwood's formula and the log-log transformation of the survival function) will also be presented at each timepoint. A Kaplan-Meier figure for survival will be displayed. Deaths will be recorded on the Death and/or survival status eCRF and the date of last subject follow-up will be determined from the maximum of eCRF visit dates (including subject survival status visit dates), and Covance laboratory collection dates.

A listing of subject deaths while on study will be provided for the mITT analysis set; subjects included in the FAS will be flagged. Days from first dose of study drug (ie, Study Day) and days from last dose of study drug (ie, Follow-up Day) for subjects for whom death occurs after stopping study drug, will be provided in the listing.

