## 6.2.8. Liver Biochemistry and Prognostic Indices

Summary statistics for the absolute value and change and percentage change from baseline for liver biochemistry tests (ALT, AST, GGT, albumin, alkaline phosphatase, total bilirubin, direct bilirubin, and INR) and prognostic indices (MELD, CPT and Maddrey's DF) will be presented by visit through Week 24 using central laboratory data except when noted otherwise (see Section 3.8.2 of the SAP for visit windows; and Section 3.6.1 for baseline MELD imputation rule when central laboratory data is not available).

Percentage change from baseline is calculated as:

([score at visit – score at baseline]  $\div$  score at baseline)  $\times$  100

An additional timepoint will be added for "Week 4 (LOCF)". For this additional timepoint, a subject will be included with their Week 4 value, or with the last chronologic value collected between Study Days 2 and 24 for subjects who are missing a Week 4 value. For all liver biochemistry tests and prognostic scores, subjects who receive a liver transplant while on study will have measurements collected up to the date of transplant included for summary tables.

Median (Q1, Q3) absolute values by visit will be plotted for MELD score, ALT, AST, total bilirubin and INR throughWeek 24 for the final analysis. Median (Q1, Q3) change and percentage change from baseline by visit will be plotted for MELD score and for total bilirubin.

A listing of values included in efficacy analyses will be provided with subjects included in the FAS flagged in listings.

Formulas for calculating each of the prognostic indices are described below:

*Maddrey DF score* = [4.6 × (PT subject [sec] – PT control [sec])] + total bilirubin (mg/dL)

Note: PT control [sec] is only available at the screening visit for each subject. For calculations over time, the subject's screening PT control [sec] will be used to calculate scores at each of the visits.

 $MELD \ score = 10 \times \{[0.957 \times Ln(Scr)] + [0.378 \times Ln(Tbil]) + [1.12 \times Ln(INR)] + 0.643)\},\$ 

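### SAP Section 6 excludes all post-transplant data from efficacy analyses, in conflict with SAP 6.2.1, SAP 6.2.7 and protocol 8.2 on death, infection and HRS

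*SAP*

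**What the plan says.** The introduction to SAP Section 6 keeps efficacy measurements up to the time of a liver transplant and then states that "data collected after transplantation will be excluded from efficacy analyses". It names no endpoint as exempt.

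SAP 6.1 lists among the secondary efficacy endpoints:
- "Number (%) of subjects who die by Study Day 28 and by Weeks 8, 12, and 24"
- "Number (%) of subjects with infection while on study"
- "Number (%) of subjects with HRS while on study"

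The sections that define these endpoints do not mention a cut at transplant:
- **Death (SAP 6.2.1).** The earliest timepoint has this rule: "subjects who die on/prior to Study Day 28 or are known to be alive through Study Day 28 will be included in the denominator"; the later timepoints follow the same pattern. For follow-up, the "date of last subject follow-up will be determined from the maximum of eCRF visit dates (including subject survival status visit dates", with central laboratory collection dates as the other source.
- **Infection and HRS (SAP 6.2.7).** Infections are summarised from first dose to the end of the study, and HRS events if reported during the study.
- **Protocol 8.2.** Deaths by Day 28 and Weeks 8, 12 and 24 are counted, with no exclusion for transplant.

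The cut is repeated only in SAP 6.2.8, for liver biochemistry and prognostic indices: "subjects who receive a liver transplant while on study will have measurements collected up to the date of transplant included for summary tables". SAP 6.2.3 handles transplant separately, as an event in transplant-free survival. SAP 6.5, which lists changes to the efficacy analysis, does not mention a post-transplant exclusion.

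**The concern.** Cutting laboratory values and prognostic scores at transplant is reasonable, because afterwards they describe a different liver. Death is another matter. If the general rule governs the mortality tables, a death after transplant is not counted. A transplanted survivor has no admissible data showing survival to the timepoint and drops out of the denominator. In the Kaplan-Meier survival analysis both subjects are censored at transplant. Infections and HRS after transplant would also be lost.

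The SAP can therefore be programmed in two ways that give different mortality results, and one of them departs from the protocol endpoint without saying so. The timing adds weight. By SAP Section 1 this plan governs the final analysis, and by SAP 2.3 treatment assignments were already unblinded for the primary analysis. The choice between the two readings should not be left to the programming stage with allocation known.

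The issue is not purely theoretical: SAP 4.2.2 has an adherence rule for "Subjects who were transplanted while on study drug" and cites a subject as an example. Treatment lasts 28 days, so even Day 28 mortality could be touched.

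**Working it through.** The plan gives no figure to reproduce. The check has two parts.

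**1. Text comparison**

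| Endpoint | Under the Section 6 rule | Under its own section |
|---|---|---|
| Death by timepoint | Post-transplant deaths and survivors drop out | SAP 6.2.1 and protocol 8.2: no transplant exception |
| Kaplan-Meier survival | Censored at transplant | SAP 6.2.1: followed to last visit, survival-status or laboratory date |
| Infection | Stops at transplant | SAP 6.2.7: to end of study |
| HRS | Stops at transplant | SAP 6.2.7: during the study |
| Laboratory tests, MELD, CPT, Maddrey's DF | Stops at transplant | SAP 6.2.8: the same |

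Only the last row agrees.

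**2. Possible size**

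Inputs:
- N = 50 per arm, from SAP 1.2 (100 subjects in the Full Analysis Set, 1:1).
- D = 15 deaths in the arm. This is assumed; 30% lies inside the short-term mortality range of about 25% to 45% quoted in protocol 1.1.
- T = transplants in the arm before the timepoint. This is assumed to be 1 or 5; the documents support only that at least one occurred in the trial.
- Dt = how many of the D deaths followed a transplant. This is assumed.

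All other subjects are taken to be followed to the timepoint.

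Mortality with everyone counted is D/N = 15/50 = 30.0%. Mortality under the literal rule is (D − Dt)/(N − T):

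| T | Dt | Literal rule | Shift from 30.0% |
|---|---|---|---|
| 1 | 0 | 15/49 = 30.6% | +0.6 points |
| 1 | 1 | 14/49 = 28.6% | −1.4 points |
| 5 | 0 | 15/45 = 33.3% | +3.3 points |
| 5 | 3 | 12/45 = 26.7% | −3.3 points |
| 5 | 5 | 10/45 = 22.2% | −7.8 points |

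The two calculations agree only when Dt/T = D/N, that is, when transplanted subjects die at the same rate as the arm as a whole. The literal rule overstates mortality if they die less often and understates it if they die more often, so neither reading is reliably conservative.

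For the comparison between arms, take 6 against 15 deaths before or without transplant, 50 per arm, and 5 transplants in the arm with 6 deaths (all assumed). The two-sided Fisher's exact test gives:
- literal rule, 6/45 v 15/50: p = 0.082
- all five survive and are counted, 6/50 v 15/50: p = 0.048
- all five die and are counted, 11/50 v 15/50: p = 0.49

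The effect on the Kaplan-Meier estimates was not calculated, because it needs event and transplant dates.

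**The case against.** The strongest defence is that the Section 6 sentence was never meant to reach death. It opens by speaking of measurements, and the one section that repeats it, 6.2.8, uses nearly the same phrase for laboratory tests and scores. SAP 6.2.1 has its own numerator, denominator and follow-up rule. Nothing in the documents makes a transplant a reason to leave the study, and transplant-free survival has its own censoring rule in 6.2.3. This has force and may well be the intended meaning. It does not settle the matter, because the operative clause says data rather than measurements, covers efficacy analyses in general, and is followed by a list that includes death.

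A second defence is that no death disappears from the report. This stands. SAP 6.2.1 lists on-study deaths for the modified intent-to-treat set, 6.2.2 lists transplants, and the adverse event overview in 7.1.6 includes all deaths during the study by treatment group. Any loss is confined to the efficacy tables and survival curves.

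A third defence is that the example counts are invented. This also stands. The arm and Full Analysis Set membership of the transplanted subject in SAP 4.2.2 cannot be seen, and with one transplant the shift is 0.6 to 1.4 points.

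A reader might go further and infer that survival was in fact censored at transplant, that this censoring was informative because transplants went to those expected to die, or that the main clinical endpoint is compromised. The documents support none of these. They do not show how the tables were run or say who was selected for transplant. They rank no secondary endpoint above another.

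**Conclusion.** The conflict is real and should be fixed. A general exclusion in SAP Section 6, taken at its word, reaches death, infection and HRS, while the sections defining those endpoints and protocol 8.2 apply no such cut and SAP 6.5 declares none. What is shown is an unreconciled rule, not a mortality result known to be wrong.

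If the rule were applied literally, with an assumed 50 subjects and 15 deaths in an arm, reported mortality would be 28.6% or 30.6% with one transplant. With five it would be 33.3% (no deaths among the five) or 26.7% (three deaths), against 30.0%. These figures rest on transplant and death counts that the documents do not give.

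The point does not threaten the primary objective. The primary endpoint is safety, results are mainly descriptive, and the Fisher test on mortality is exploratory.

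**What to change.** In SAP Section 6:
- Limit the post-transplant exclusion to laboratory tests, Lille score, MELD, CPT, Maddrey's DF and fibrosis markers.
- State that death by each timepoint and Kaplan-Meier survival (Tables 15.9.1.1 to 15.9.1.3 and 15.9.1.5, with supporting listings 15.9.1.4 and 15.9.1.6) count every death, and keep transplanted subjects in the denominator and at risk after transplant.
- State that infection and HRS follow the windows in SAP 6.2.7.
- Keep transplant-free survival (SAP 6.2.3) as the analysis that treats transplant as an event.

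If the sponsor does intend the exclusion to cover death, SAP 6.5 should declare it as a change from protocol 8.2, and SAP 6.2.1 should carry the rule.

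The cost is a few lines of text. No new data are needed: the survival status form and the protocol's phone contacts (6.3.4, 6.5.2, 6.5.3) already provide for collecting vital status. The edit should be made before the SAP is finalised. If that has already happened, the reading used should be recorded in the clinical study report, as SAP Section 1 provides for later changes.

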## 6.1. Secondary Efficacy Endpoints:

- Number (%) of subjects who die by Study Day 28 and by Weeks 8, 12, and 24
- Number (%) of subjects receiving a liver transplant by Study Day 28 and by Weeks 8, 12, and 24
- Summary of Lille score by visit through Week 4
- Number (%) of subjects with Lille response (score < 0.45) at Day 7 (eg, Week 1)
- Number (%) of subjects with Lille null response (score  $\ge 0.56$ ) at Day 7 (eg, Week 1)
- Mortality Risk at Months 2 and 6 based on Lille score response at Day 7 (eg, Week 1) and the baseline MELD score (continuous)
- Number (%) of subjects with infection while on study
- Number (%) of subjects with HRS while on study
- Length of initial hospital stay
- Change from baseline in liver biochemistry tests (ALT, AST, GGT, albumin, alkaline phosphatase, total bilirubin, direct bilirubin, and INR) by analysis visit through Week 24
- Change from baseline in prognostic indices (MELD, CPT, and Maddrey's DF) by analysis visit through Week 24

#### 6.2. Analysis Methods for Secondary Efficacy Endpoints

#### 6.2.1. Death

The number (%) of subjects with a death by Study Day 28, and by Weeks 8, 12, and 24 will be displayed by treatment group. For the endpoint death by Day 28, subjects who die on/prior to Study Day 28 or are known to be alive through Study Day 28 will be included in the denominator for calculation of percentage of subjects with death. Subjects not followed through Day 28 will be summarized by their reason for premature discontinuation from study. A 2-sided

Fisher's exact test will be used to explore whether there are differences between treatment groups in percentage of subjects with death by Day 28. Deaths by Weeks 8, 12, and 24 will be summarized in the same manner as deaths by Study Day 28. Kaplan-Meier estimates of survival and the 95% CI (based on Greenwood's formula and the log-log transformation of the survival function) will also be presented at each timepoint. A Kaplan-Meier figure for survival will be displayed. Deaths will be recorded on the Death and/or survival status eCRF and the date of last subject follow-up will be determined from the maximum of eCRF visit dates (including subject survival status visit dates), and Covance laboratory collection dates.

A listing of subject deaths while on study will be provided for the mITT analysis set; subjects included in the FAS will be flagged. Days from first dose of study drug (ie, Study Day) and days from last dose of study drug (ie, Follow-up Day) for subjects for whom death occurs after stopping study drug, will be provided in the listing.

# 6.2.2. Liver Transplantation

The number (%) of subjects with liver transplantation by Study Day 28, and by Weeks 8, 12, and 24 will be displayed by treatment group. For the endpoint liver transplantation by Day 28, subjects undergoing liver transplantation by Study Day 28 or who are known to still be on study through Day 28 will be included in the denominator for calculation of percentage of subjects with liver transplantation. Subjects not followed through Day 28 will be summarized by their reason for premature discontinuation from study. Liver transplantation by Weeks 8, 12, and 24 will be summarized in a similar manner. Liver transplants will be recorded on the survival status eCRF.

A listing of liver transplants while on study will be provided for the mITT analysis set; subjects included in the FAS will be flagged. Days from first dose of study drug (ie, Study Day) and days from last dose of study drug (ie, Follow-up Day) for those transplanted after stopping study drug will be provided in the listing.

## 6.2.3. Transplantation-free survival

Time up to the first liver transplant or death event (in days) will be calculated as:

(first of date of liver transplant/death - randomization date + 1)

Data from surviving subjects with no transplant will be censored at the last date that the subject is known to be alive and transplant-free (maximum of central laboratory dates and eCRF [including survival status] visit dates).

In the following SAS code, *Days* is the number of days from randomization date to the first death/liver transplant or to the date of last study visit if no death or liver transplant has been observed. *Status* is a binary variable with 1 representing no death and no transplant observed and 0 representing that there is a death or transplant that has been observed.

```
proc lifetest data=txfs_2groups timelist= 28 56 84 168 conftype=loglog alpha=0.05 ;
   Time Days*Status(1);
   Strata = trtgrp;
run;
```

For each treatment group, the Kaplan-Meier (KM) estimates of transplant-free survival at Day 28, and at Weeks 8, 12, and 24 and the 95% CI will be provided. The 95% CI will be calculated based on Greenwood's formula and log-log transformation of the survival function.

A figure of the KM curve for transplant-free survival will be provided.

The median, Q1 and Q3 of the transplant-free survival will be provided for each treatment group. The 95% CI for median transplant-free survival is based on Brookmeyer-Crowley method of inverting a generalization of the sign test for censored data will also be provided for each treatment group.

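### SAP 6.2.3 gives two censoring dates for transplant-free survival; the one in the definition of Days can only raise the Kaplan-Meier event risk, by an amount that is probably small

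*SAP*

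**What the plan says.** SAP 6.2.3 computes time to event as "first of date of liver transplant/death - randomization date + 1". Surviving subjects without a transplant "will be censored at the last date that the subject is known to be alive and transplant-free", and that date is the "maximum of central laboratory dates and eCRF [including survival status] visit dates".

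The next paragraph defines the input to PROC LIFETEST. For subjects without an event, Days runs from randomization "to the date of last study visit if no death or liver transplant has been observed". This sentence mentions neither survival-status dates nor laboratory dates.

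For overall survival, SAP 6.2.1 follows the broader rule: "the date of last subject follow-up will be determined from the maximum of eCRF visit dates (including subject survival status visit dates", with central laboratory collection dates added.

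Events do not depend on clinic attendance. SAP 6.2.1 states: "Deaths will be recorded on the Death and/or survival status eCRF". SAP 6.2.2 states: "Liver transplants will be recorded on the survival status eCRF".

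**The concern.** The two sentences name different dates for the same subjects, and a programmer would normally build Days from its own definition. Under that definition, information obtained outside a visit is used when the outcome is bad and dropped when it is good. Risk sets shrink only through event-free subjects, so the estimated event risk goes up.

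Two things are at stake. The survival tables (15.9.1.3 and 15.9.1.5) and the transplant-free survival tables (15.9.1.7 and 15.9.1.9) would rest on different follow-up for the same subjects, so the gap between the curves would no longer reflect transplants alone. If the arms differed in visit attendance, the excess would also differ between arms. In addition, this SAP governs the final analysis, after treatment was unblinded for the primary analysis (SAP 2.3), so the choice between two written rules should not be left open.

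**Working it through.** The documents give no numerical estimate for this endpoint, so there is no figure to reproduce. The check has four steps.

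**1. Do the two dates differ in practice?** SAP Section 1 lists the Week 24 study visit and the Week 24 subject status form as separate items. Protocol 6.7 names follow-up visits and phone contact separately. Protocol 6.3.4, 6.5.2 and 6.5.3 require a call about mortality and transplantation when the Week 4, 8, 12 or 24 visit falls before Day 28, 56, 84 or 168. Status dates later than the last visit are therefore expected. Those four days are also the time points at which 6.2.3 reports estimates.

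**2. Direction.** The Kaplan-Meier estimate is S(t) = product over event times of (1 − d_i/n_i), with d_i events among n_i at risk. Both rules have the same d_i. The last-visit rule can only move the censoring of event-free subjects earlier, so each n_i is equal or smaller and 1 − S(t) is equal or larger.

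**3. Hand example (illustrative).** Take 50 subjects, with 10 events on Day 10 and 5 on Day 100. Of the 35 survivors, 10 have a last visit on Day 28 but are known event-free to Day 170.
- Last-known-event-free rule: 1 − (40/50)(35/40) = 30.0% at Day 168.
- Last-visit rule: the 10 are gone before Day 100, so 1 − (40/50)(25/30) = 33.3%.

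**4. Simulation of the size.** Inputs from the documents:
- 50 subjects per arm (100 in the Full Analysis Set, 1:1; SAP 1.2).
- Risk of 20% by Day 28 (one-month mortality on prednisolone, Protocol 1.1).

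Assumptions:
- True risk at Day 168 of 30% or 40%. Protocol 1.1 gives short-term mortality of about 25% to 45%.
- A share q of subjects stop visits at a uniform time between Days 28 and 140 but have status known at Day 168. No document gives q.

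Mean excess of the last-visit rule at Day 168, in percentage points:

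| q | true risk 30% | true risk 40% |
|---|---|---|
| 5% | 0.3 | 0.5 |
| 10% | 0.6 | 1.0 |
| 20% | 1.3 | 2.2 |
| 30% | 2.1 | 3.5 |

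The excess at Days 56 and 84 is below about 1 point throughout this range, and Day 28 is unchanged.

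If every subject attends Week 24 within ±5 days, and those seen before Day 168 are phoned between Days 168 and 175, the Day 168 excess is about 0.1 to 0.4 points. It is then zero at Days 56 and 84.

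For scale, the standard error of one arm's estimate is about √(0.3 × 0.7/50) = 6.5 points at 30% risk and √(0.4 × 0.6/50) = 6.9 points at 40%. The largest table entries are 2.1/6.5 = 0.3 and 3.5/6.9 = 0.5 standard errors. If two arms with the same 40% risk had q = 10% and q = 30%, the spurious gap would be 3.5 − 1.0 = 2.5 points.

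**The case against.** The best defence is that the correct rule stands immediately before the disputed sentence, which only explains variable names. The SAP also calls status contacts visits in both 6.2.1 and 6.2.3, so last study visit may be shorthand for the rule just given. The PROC LIFETEST statements themselves contain no censoring rule. This is a fair reading of intent. It does not settle the text, because SAP Section 1 separates the visit from the status form, and the Days sentence also omits laboratory dates.

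The defence is stronger on size. The planned calls follow visits made slightly early, within windows of ±3 days at Week 4 and ±5 days at Weeks 8, 12 and 24, so they close gaps of days rather than months. Protocol 6.7 asks subjects with confirmed disease who stop drug early to attend all remaining visits. SAP Section 1 allows a status form in place of the Week 24 visit but does not say how often that occurs.

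A reader might infer a distortion of 4 to 5 points, present at Weeks 8, 12 and 24 alike. The documents do not support that. Such figures (4.3 points at 30% risk and 4.9 at 40%, with q = 30%) need a constant hazard. At 30% risk, a constant hazard implies only 1 − 0.7^(28/168) = 6% by Day 28, against the protocol's own 20%. Even under a constant hazard with q = 30%, the excess is at most 0.2 points at Day 56 and 0.8 at Day 84.

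The consequence is also limited. The primary endpoint is safety, transplant-free survival is not in the SAP 6.1 list, and 6.2.3 specifies estimates and intervals without a between-arm test. The supporting listings (15.9.1.8 and 15.9.1.10) would show each subject's days and censoring status.

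**Conclusion.** The sentence defining Days is wrong as written, with low impact. That 6.2.3 contains two censoring dates is a matter of text, and the direction of the effect follows from the estimator: equal or higher event risk, never lower.

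The size is conditional. It is zero unless an event falls between some survivor's last visit and a later status or laboratory date. It is a few tenths of a point at Day 168 with attendance inside the windows, and up to about 2.1 points (30% risk) or 3.5 points (40% risk) if as many as 30% of subjects stop visits early but are traced to Week 24. These figures rest on the assumed q, the assumed 24-week risk and 20% risk by Day 28. The documents do not show that the estimates will in fact be overstated, since the programmer may follow the prose.

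**What to change.** In SAP 6.2.3, redefine Days as the time from randomization to the first death or transplant, plus 1 as in the formula above it (the Days sentence leaves out the + 1). For subjects without an event, run it to the last date known event-free, using the rule already stated in that section: the latest of central laboratory dates and eCRF visit dates, survival status included. State that the 6.2.1 survival curves draw the last-contact date from the same sources.

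The cost is one sentence and one derived variable. No new data are needed.
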